The efficacy and safety of carrimycin treatment in patients with novel coronavirus infectious disease (COVID-19) : A multicenter, randomized, open-controlled study

Study protocol

Version No.:	V5.0			
Version date:	February 20, 2020			
	Beijing YouAn Hospital, Capital Medical			
	University			
	Shenyang Tonglian Group Co., Ltd.			
	Institute of Medicinal Biotechnology, Chinese			
	Academy of Medical Sciences			
	Huangshi Central Hospital			
	Shenyang Pharmaceutical University			
	The First Affiliated Hospital of Chongqing			
Study sites:	University of Medical Science			
	The Second Affiliated Hospital of Harbin			
	Medical University			
	No.2 People's Hospital of Fuyang City			
	The First Affiliated Hospital of Bengbu			
	Medical College			
	Renmin Hospital of Wuhan University			
	The Six People's Hospital of Shenyang			
	Nanyang Central Hospital			
Principal investigators:	Director [name]			

Project Consultant: Academician [name]

Confidentiality

This clinical study protocol is a confidential document for the purpose of this clinical study and shall not be disclosed to anyone other than the investigators involved and members of the institutional review board.

Synopsis

	The efficacy and safety of carrimycin treatment in patients with novel						
Name of study	coronavirus infectious disease (COVID-19): A multicenter,						
	randomized, open-controlled study						
	Evaluate the efficiency and safety of Carrimycin in the patients with						
Study Objectives	2019-nCoV pneumonia, establish the criteria for clinical cure and						
	the early predictive model of COVID-19 progression.						
	A randomized, open, positive-controlled and multi-center clinical						
Study design	study						
Planned sample	500 subjects along a						
size	520 subjects planned.						
	Subjects shall meet all the following criteria before being						
	included:						
	Inclusion criteria						
	(1) Subjects or their legal representatives have signed the informed						
	consent form(ICF); agree not to participate in other clinical						
	studies within 30 days after the last administration from the first						
	administration of the study drug.						
	(2) Subjects are aged \geq 18 and \leq 75;						
	(3) Meet the diagnostic criteria for 2019-nCoV pneumonia (V5.0);						
Inclusion/exclusion	(4) SOFA score: 1 ~ 13 points.						
criteria	(5) A retreated patient or the relapsed patient meets any of the						
	following criteria:						
	1 Have fever again or aggravated clinical symptoms; 2						
	2019nCOVRNA in the throat swabs converts from negative to						
	positive; ③ The clinical symptoms don't improve or						
	2019nCOVRNA continues to be positive; ④ The chest CT						
	shows pneumonia or fibrosis progression.						
	Clinical stratification:						
	1. Mild type: clinical symptoms mild or asymptomatic, no						

pneumonia performance in CT, but positive 2019-nCoV in throat
swabs or gargle.
2. Ordinary type: fever, respiratory symptoms, etc., pneumonia
performance visible in CT.
3. Severe type: meeting any of the following criteria:
(1) Respiratory distress, RR≥30 times/min;
(2) Finger oxygen saturation ≤93% in rest state;
(3) Arterial partial pressure of oxygen (PaO2)/concentration of
oxygen inhalation (FiO2)≤300mmHg (1mmHg=0.133kPa).
4. Critical type: meeting any of the following criteria:
(1) Respiratory failure occurs and mechanical ventilation is
required;
(2) Patients go into shock;
(3) ICU is needed for other organ failure.
Exclusion criteria
(1) Other viral pneumonia
(2) Patients who have received tumor immunotherapy (such as
PD-1/L1, CTLA4, etc.) in the past 1 month, and inflammatory
factor modulators such as Ulinastatin;
(3) Patients who have taken anti-bacterial drugs such as macrolide
in the past 1 week;
(4) Patients who have received organ transplantation or surgery
planning in the past 6 months;
(5) Patients who can't take food or drugs due to coma or intestinal
obstruction;
(6) Patients who have severe underlying diseases that affects
survival, including uncontrolled malignant tumor with multiple
metastases that cannot be resected, blood diseases, dyscrasia,
active bleeding, severe malnutrition, etc.
(7) Women subjects that are pregnant or lactating, or subjects
(including male subjects) having a pregnancy plan (including

		plans for sperm donation or egg donation), or subjects that may
		fail to take effective contraceptive measures within the next 6
		months;
		(8) Patients with allergic constitution, or patients allergic to
		macrolides and lopinavir/ritonavir tablets;
		(9) Patients with contraindications to lopinavir/ritonavir tablets who
		plan or are using drugs that interact with the drug (including:
		drugs that are highly dependent on CYP3A clearance and
		whose elevated plasma concentrations can be associated with
		severe and/or life-threatening events [with a narrow therapeutic
		index], CYP3A inducer [see instruction for details]) and cannot
		stop using or use other drugs instead;
		(10)Patients whose ALT/AST levels are 5 times higher than the
		normal upper limit and total bilirubin is 3 times higher than the
		upper limit of normal, or patients with child-Pugh grade C
		cirrhosis.
		(11)ECLS (ECMO, ECCO2R, RRT)
		(12)Critical patients with expected life \leq 48 hours
		(13)Patients who have participated in any other clinical study within
		1 month;
		(14) The investigators conclude that the patients not suitable for the
		study.
		The trail group and the control group were randomized according to
		1: 1.
		(1) Trial group: basic treatment + Carrimycin
Trial drugs a	nd	Mild type: 0.4g of Carrimycin tablets, p.o. after meal once a day for 7
medication		consecutive days, followed up for observation after the end of
methods		treatment.
		Ordinary type: 0.4g of Carrimycin tablets, p.o. after meal once a day
		for 10 days, followed up for observation after the end of treatment.
		Severe and critical: 0.4g of Carrimycin tablets, p.o. after meal once
		a day for 14 consecutive days. If oral administration is not possible,

	the drug should be administered through a nasal feeding tube.
	For the combination drugs of basic treatment according to the
	Diagnosis and Treatment Program for 2019-nCoV (V5.0,Chinese)
	 (2) Control group: any of basic treatment + lopinavir/ritonavir tablets or Arbidol or chloroquine phosphate: Mild and ordinary type: 400mg/100mg, bid of lopinavir/ritonavir
	tablets each time: or 500mg bid of chloroguine phosphate: or 200mg
	tid of Arbidel for 7 consecutive days, followed up for absorvation
	after the end of treatment.
	Severe and critical type: 400mg/100mg, bid of lopinavir/ritonavir
	tablets each time; or 500mg bid of chloroquine phosphate; or 200mg
	tid of Arbidol for 10 consecutive days, followed up for observation
	after the end of treatment.
	For the combination drugs of basic treatment according to the
	Diagnosis and Treatment Program for 2019-nCoV (V5.0,Chinese)
	Permitted therapy combination and/or drug combination:
	Clinical treatment schemes other than antiviral therapy in the
	Diagnosis and Treatment Program for 2019-nCoV (V5.0,Chinese) are permitted.
	Acetaminophen (paracetamol), diclofenac sodium suppositories,
	lyripine (lysisin aspirin) antipyretics are prohibited.
Therapy/drug	
combination	Prohibited therapy combination and/or drug combination:
	No other antiviral drugs or antibiotics are allowed during the trial
	(except retreated or relapsed patients or in severe and critical type
	cases).
	Keep a detailed record of the dugs combination, especially the
	glucocorticoids.
Observation and its i	Screening period: -2 days~ 0 day;
Observation period	Treatment period: 7-14 days;

	Follow-up observation period: follow up to 30 days after the first							
	administration.							
	Primary efficiency indicators							
	(1) Fever to normal time (day)							
	(2) Pulmonary inflammation resolution time (HRCT) (day)							
	(3) Negative conversion (%) of 2019-nCOVRNA in gargle (throat							
	swabs) at the end of treatment							
	Secondary efficiency indicators							
	(1) Negative conversion ratio of 2019-nCOVRNA in gargle (throat							
	swabs), urine and stool on Day 1, 3, 5 and 14 after							
	administration;							
	(2) Progress rate of 2019-nCoV pneumonia							
	(3) Changes in immune-related indicators (lymphocyte count,							
	lymphocyte percentage, counts and percentages of CD4 and							
	CD8, and inflammatory cytokines) from baseline on Day 1, 3, 5							
	and 7-10 after administration.							
Effectiveness	(4) Changes in SOFA score from baseline on Day 1, 3, 5 and 7-10							
indicators	after administration;							
	(5) Changes in white blood cell count from baseline on Day 1, 3, 5							
	and 7-10 after administration;							
	 (6) Changes in PCT and C-reactive protein from baseline on Day 1, 3 5 and 7-10 after administration: 							
	(7) Changes in CT features from baseline on Day 7-10 and 14 after							
	administration;							
	(8) Length of stay in hospital and mortality rate.							
	There are currently criteria for release from clinical isolation and							
	discharge on 2019-nCoV pneumonia (V5.0,Chinese), and there is							
	no "gold standard" for clinical cure, and it is difficult to obtain the							
	basis for pulmonary diagnosis. Therefore, the following criteria are							
	currently used clinically (empirical evidence, lack of scientific							
	evidence) and it is not known whether there is a chronic infection or							

	virus carrying. Therefore, the following criteria are used for the					
	clinical assessment in this project:					
	Criteria for clinical cure:					
	1) The clinical symptoms disappear and the quality of life is					
	normal.					
	2) Lung CT/HRCT is normal.					
	3) T lymphocyte function and count return to normal.					
	4) Negative 2019-nCOV in secretions (gargle, urine and stool)					
	Clinical chronic or complications:					
	1) Gastrointestinal and respiratory symptoms completely					
	disappear, the quality of life is lowered (anxiety, insomnia and					
	other mental disorders) or the lung CT/HRCT lesions exist, or					
	lung fibrosis is formed.					
	2) Or laboratory abnormalities (blood routine, T lymphocyte count					
	or function).					
	3) Negative 2019-nCOV in secretions (gargle, urine and stool)					
	(1) AE, SAE.					
	(2) Vital signs: breath, blood pressure, heart rate, body					
	temperature.					
	(3) Laboratory examination: blood routine (WBC, RBC, Hb, HCT, PLT,					
Safety indicators	LY and LY%), urine routine (WBC, RBC, Pro), blood					
	biochemical examinations (ALT, AST, TBIL, ALP, GGT, Cr, BUN,					
	Glu) and coagulation function (PT, APTT, TT, FIB).					
	(4) Routine ECG: heart rate, Q-Td, ST segment and T wave					
	changes.					
	(1) General principle					
	1) Description of statistics					
	The primary indicators collected in this study are described with					
Statistical analysis	statistical method. Quantitative indicators are described by means of					
	mean, standard deviation, median, quartile, maximum, minimum					
	and the like; qualitative indicators are described by frequency,					
	percentage and the relationship.					

2) Statistical test
Unless otherwise specified, the statistical significance level is
0.05 by two-sided test (one-sided 0.025) and the 95% confidence
interval shall be provided for the estimation of inter-group variance
parameters.
3)Random grouping: The hierarchical random grouping method
is adopted
(2) Characteristics of cases
1) Subject distribution
1 The population and the number of enrolled and completed
cases in each center are listed, and three analysis data sets
(FAS, PPS, SS) are determined.
② A detailed list of the data set categories is made.
${}^{\textcircled{3}}$ The number and ratio of subjects who are randomly
enrolled, complete the trial, and withdraw from the trial early
and the reasons are calculated.
④ The subject distribution flow chart is plotted.
2) General information and baseline characteristics
The demographic information, previous medication history and
history of other diseases of the patients are described with statistical
method. General information and baseline characteristics are
described based on FAS.
(3) Analysis of drug exposure and drug combination
Analysis based on SS.
1) Drug exposure, dose intensity and exposure time of each
group are calculated.
2) The drug combination is coded by WHO ATC and
summarized according to the ATC secondary classification
and PT. The number and ratio of cases are calculated.

(4) Efficiency analysis

Analysis based on FAS and PPS.

The primary effective indicator are:(1) Fever to normal time (day),(2)Pulmonary inflammation resolution time (HRCT) (day),(3)Negative conversion (%) of 2019-nCOVRNA in gargle (throat swabs) at the end of treatment on Days 7-10 after administration. The statistical significance level is set to one-sided 0.025. The two-sided 95% confidence interval (95%CI) are confidence calculated. The interval is estimated bv Miettinen-Nurminen.

The secondary efficiency indicators include negative conversion ratio of 2019-nCOVRNA from samples, immune-related indicators (lymphocyte count, lymphocyte percentage, counts and percentages of CD4 and CD8), SOFA score, white blood cell count, C-reactive protein, pulmonary imaging improvement indicators and complete antipyresis time on Day 1, 3, 5 and 14 after administration. In-hospital time, clinical cure ration and mortality are also analysed. The secondary efficiency indicators are subject to descriptive statistical analysis according to the data type.

(5) Safety analysis

SS data sets are used for safety analysis.

- 1) Adverse events are coded according to the MedDRA.
- 2) The occurrence of adverse events/reactions, serious adverse events/reactions and adverse events/reactions resulting in drop out is summarized and analyzed in the form of a frequency table (number of cases, case, and incidence).
- 3) The occurrence of varying severity orders of adverse events/reactions, serious adverse events/reactions and adverse events/reactions resulting in drop out is subject to descriptive statistical analysis in the form of a frequency

	Screenin g period		Med	dication pe	follow-up observation period		Forte		
Study stage	Day -2 ~ day 0 (baselin e)	Day 1	Day 3	Day 7	Day 10	Day 14	Day 14 ±1 days	Day 28 ± 2 days	Early withdrawal
Visit	1	2	3	4	5	6	7	8	
Informed consent form	×								
Demographic information	×								
Medical data	×	×	×	×	×	×	×	×	
Vital signs	×	×	×	×	×	×	×	×	×
SOFA score	×		×	×	×	×		×	
Physical examination	×	×	×	×	×	×	×	×	×
Review of inclusion/excl usion criteria	×	×							
Blood routine ³	×		×	×	×	×	×	×	×
Urine routine ⁴	×		×	×	×	×	×	×	×
Blood biochemistry ⁵	×		×	×	×	×	×	×	×
Coagulation function ⁶	×		×	×	×	×			×
T cell subset and cytokines 7	×		×	×	×	×	×	×	×
C-reactive protein	×		×	×	×	×			×
2019-nCOVRNA in throat swabs, urine and stool	×	×	×	×	×	×	×	×	×
Chest imaging (CT)	×			×	×	×	×	×	×
12-lead ECG	×			×	×	×			×
Pregnancy test ⁸	×							×	×
Enrollment		×							
Administration		×	×	×	×	×			

Flow chart of clinical trial

	Screenin g period		Meo	dication p	follow-up observation period				
Study stage	Day -2 ~ day 0 (baselin e)	Day 1	Day 3	Day 7	Day 10	Day 14	Day 14 ±1 days	Day 28 ± 2 days	Early withdrawal
Visit	1	2	3	4	5	6	7	8	
Record of clinical treatment scheme	×	×	×	×	×	×	×	×	×
Trial drug dispensing		×	×	×	×	×			
Trial drug recovery		×	×	×	×	×			×
Combination therapy	×	×	×	×	×	×	×		
Reserve throat swabs	×	×	×	×	×	×	×	×	×
Reserve blood specimens (serum, plasma and cells)	×	×	×	×	×	×	×	×	×
Reserve urine and stool	×	×	×	×	×	×	×	×	×
Adverse event	×	×	×	×	×	×	×	×	×

Notes:

1. Visit 1 (screening period) and visit 2 (baseline) may be on the same day, and Day 0 is the first day of administration;

2. To withdraw from the trial in advance, it is necessary to complete the last visit items; in case of AE at the end of the trial, follow-up should be conducted according to the "AE" requirements of the protocol;

- 3. Blood routine examinations: including WBC, RBC, Hb, HCT, PLT, LY, LY%;
- 4. Urine routine examinations: including WBC, RBC, Pro;
- 5. Blood biochemical examinations: including ALT, AST, TBIL, ALP, GGT, Cr, BUN, Glu;
- 6. Coagulation function: including PT, APTT, TT, FIB;
- 7. T cell subset: counts and percentages of CD4+ and CD8+;

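### The antibiotic ban makes no exception for bacterial infection in first-treated mild and ordinary patients; separately, PCT is a secondary indicator that no visit schedules

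*Protocol*

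**What the plan says.** All places are in the Protocol; no SAP was at hand.

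- **Synopsis, Therapy/drug combination, prohibited therapy.** "No other antiviral drugs or antibiotics are allowed during the trial", with one exception in brackets: "except retreated or relapsed patients or in severe and critical type" cases.
- **Same row, permitted therapy.** The clause allows "Clinical treatment schemes other than antiviral therapy in the" national Diagnosis and Treatment Program (V5.0), and then bars several named antipyretics.
- **Exclusion criteria.** Criterion (1) reads "1) Other viral pneumonia". Criterion (3) removes "Patients who have taken anti-bacterial drugs such as macrolide" in the past week. Criterion (8) covers allergy to "macrolides and lopinavir/ritonavir tablets". Criterion (14), "14) The investigators conclude that the patients not suitable for the" study, leaves the investigator free to refuse a patient.
- **Flow chart, note 2.** "To withdraw from the trial in advance, it is necessary to complete the last visit items".
- **Effectiveness indicators, secondary (6).** Change from baseline in PCT and C-reactive protein is to be assessed. The flow chart has a row for C-reactive protein and none for PCT.

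**The concern.** The exemption follows how ill the patient is and whether the patient was treated before. The usual reason for giving an antibiotic, a bacterial infection, plays no part. An exempt patient may receive one with no stated indication, while a non-exempt patient with an infection may not.

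First, this affects the care of the individual patient. Second, it affects uniform conduct across many sites. Faced with the same infection, one site may follow the clause and withhold, another may treat in breach of it, and a third may withdraw the patient. Withdrawal would cut short observation of the time to normal temperature and the time to CT resolution, both primary indicators.

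PCT matters for a different reason: a declared secondary indicator has no scheduled measurement.

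**Working it through.** The main point needs no formula. It follows from applying the clauses in turn.

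**1. Who may receive an antibiotic.**

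| Patient | Antibiotic under the clause | Infection required? |
|---|---|---|
| Retreated or relapsed, any type | allowed | not stated |
| Severe or critical | allowed | not stated |
| First-treated, mild or ordinary | barred | no exception even if present |

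**2. Whether the third group exists.** Inclusion criterion (5) stands in a list of which all items must be met. Read literally, every subject would be retreated or relapsed and the ban would bind nobody. But the ban exempts retreated and relapsed patients by name, which presupposes others who are neither. I read criterion (5) as applying only to patients who are retreated or relapsed.

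**3. Whether entry criteria remove the problem.** Exclusion (1) concerns viral pneumonia only. Exclusion (3) concerns recent antibacterial use, not infection. Exclusion (14) acts at entry and cannot help with an infection that arises later.

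**4. Whether early withdrawal solves it.** Note 2 says what must be done on leaving. It takes the patient out of the trial and gives no means of treating within it.

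**5. How many patients.** From the synopsis: 500 subjects randomised 1:1, so 250 per arm (a figure of 520 also appears). Assumed, because the documents do not give them: 50 to 150 first-treated mild or ordinary patients per arm, and a risk of bacterial infection of 1 to 10%.

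Expected patients, both arms = 2 × (number per arm) × risk:

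- Low: 2 × 50 × 0.01 = 1, or 1/500 = 0.2% of the trial
- Middle: 2 × 100 × 0.05 = 10, or 10/500 = 2%
- High: 2 × 150 × 0.10 = 30, or 30/500 = 6%

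Chance of at least one such patient: low 1 − 0.99^100 = 0.634; middle 1 − 0.95^200, above 0.999. Even at the low end the situation is more likely than not to occur. The percentages are also the share of the trial that would be lost if every such patient were withdrawn.

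**6. PCT.** Secondary indicator (6) names PCT and C-reactive protein together. The flow chart lists C-reactive protein at screening, Days 3, 7, 10 and 14, and early withdrawal. PCT has no row, and notes 3 (blood routine) and 5 (biochemistry), which itemise their panels, do not include it. The indicator therefore cannot be obtained from the visits as scheduled.

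**The case against.** **The clauses conflict.** A reader might infer that the permitted and prohibited clauses contradict each other, because the permission carves out antivirals but not antibiotics. The documents do not support this. The ban is explicit and specific, and the same row already limits the general permission by barring named antipyretics, so the natural reading is that the specific ban governs. A true conflict would need the Program to include antibiotics, and the Program is not reproduced.

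**Carrimycin gains an unfair advantage.** A reader might also infer that the ban favours carrimycin on fever and CT outcomes, because only controls would lack antibacterial cover. Exclusions (3) and (8) suggest that the drug is handled as a macrolide, but its antibacterial action is nowhere stated. The ban is formally the same in both arms. Any size put on such a bias would rest almost wholly on assumed inputs.

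**The rule may be elsewhere.** The text at hand is a synopsis and flow chart that stop at note 7, and note 2 refers to adverse event requirements that are not shown. Handling of an infection could sit there. That is fair, but such a rule would still contradict an explicit ban in the synopsis, which would have to be brought into line.

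**The group is narrow.** An infection that makes a patient severe or critical would bring the exemption into play if type is judged at that time; the text does not fix type at baseline. This stands as a limit on the number affected. It does not cure the rule, since the patient would have to deteriorate before an antibiotic was allowed.

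**PCT is a different matter.** Agreed. It does not show that the ban is defective and is raised separately. The list of secondary indicators in the statistical analysis section also omits PCT, but that list need not be exhaustive, so nothing is built on it.

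**Conclusion.** As worded, the prohibited-therapy clause forbids an antibiotic for a bacterial infection arising on trial in a first-treated mild or ordinary patient. This rests on reading inclusion (5) as conditional, which is the only reading that gives the ban any effect. It is a patient-care and uniform-conduct defect, worth correcting because the correction is simple. The expected number affected is 1 to 30 across both arms under the stated assumptions, and no material bias between arms can be shown from the documents. The missing PCT row is a separate scheduling inconsistency that can be read directly from the flow chart.

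**What to change.** 1. Extend the exception, in both arms, to: or suspected or documented bacterial infection as judged by the investigator, avoiding macrolides where an alternative exists. Treatment should not depend on a PCT level or a culture result, since either condition would still bar treatment of some clinically evident infections.
2. State that an antibiotic given on this ground is not a protocol deviation and does not require withdrawal.
3. Record the indication for each antibiotic and report antibiotic use by arm within the combination-drug (ATC) summary already planned.
4. Separately, add a PCT row to the flow chart on the C-reactive protein days. Those days cover screening and Days 3, 7 and 10, but not Days 1 and 5, which secondary indicator (6) also names.

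The cost is one clause, one sentence, an indication field in a record already kept, and one laboratory test at existing visits. The downside is that, in an open trial, controls may be given antibiotics somewhat more readily. The by-arm report would show this but would not prevent it.

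### Viral-negativity primary endpoint has no single reading day: end of treatment falls 3 to 4 days later on carrimycin than on control in two of three dosing groups, and conflicts with the Days 7-10 window

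*Protocol*

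**What the plan says.** The endpoint's timing is stated twice in the protocol synopsis.

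- **Effectiveness indicators, primary indicator (3):** negative conversion in gargle or throat "swabs) at the end of treatment", with no day given.
- **Statistical analysis, (4) Efficiency analysis:** "3)Negative conversion (%) of 2019-nCOVRNA in gargle (throat swabs) at the end of treatment on Days 7-10 after administration".

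End of treatment depends on arm and type (Trial drugs and medication methods):

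- **Carrimycin:** mild type 7 days; ordinary type "for 10 days, followed up for observation after the end of treatment"; severe and critical "a day for 14 consecutive days".
- **Control:** mild and ordinary type "tid of Arbidel for 7 consecutive days, followed up for absorvation"; severe and critical "tid of Arbidol for 10 consecutive days, followed up for observation". The same durations apply to the other two control drugs.

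Elsewhere the synopsis uses Day 7-10 as if it were a nominal time point, for example "7) Changes in CT features from baseline on Day 7-10 and 14 after". Secondary indicator (1), the other RNA endpoint, is read in throat "swabs), urine and stool on Day 1, 3, 5 and 14 after" administration. The flow chart has separate Day 7 and Day 10 visits and no combined one. It marks RNA sampling at every visit without distinguishing the arms.

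**The concern.** A conversion proportion compares two arms fairly only if both are read at the same time since randomisation or first dose. Here the reading is tied to the end of a course that is longer on carrimycin for every type except mild. RNA negativity becomes more common as days pass, so the arm read later looks better even if the drugs are equivalent.

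The added window makes the definition inconsistent as well. A 14-day course cannot end on Days 7-10, so for severe and critical carrimycin patients the two halves of the sentence cannot both hold. For ordinary type both halves hold, and they yield Day 10 against Day 7.

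The study is open-label and this is a primary endpoint. Leaving several admissible reading days, with the choice possibly made after data are seen, is a further risk.

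**Working it through.** **Step 1. Reading days from the protocol alone.**

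| Type | Carrimycin ends | Control ends | Gap | Both inside Days 7-10? |
|---|---|---|---|---|
| Mild | 7 | 7 | 0 | yes |
| Ordinary | 10 | 7 | +3 | yes, on different days |
| Severe/critical | 14 | 10 | +4 | no, carrimycin is outside |

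This needs no assumption. The direction of the bias needs only that negativity rises with time.

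**Step 2. Inputs for the size.** From the protocol: 1:1 allocation, one-sided 0.025, and 500 subjects, hence 250 per arm. The synopsis also gives 520; 260 per arm raises the rates below only slightly. The text states no expected conversion rates, margin or power, so there is no protocol figure to reproduce here. *Assumed:* the same exponential clearance in both arms, medians of 7-14 days, conversion that does not reverse, and the type mixes shown.

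**Step 3. Formulas.** P(negative by day t) = 1 − 2^(−t/median). Arm rates pT (carrimycin) and pC (control) are averages weighted by type, and p̄ is their mean. With Δ = pT − pC, s0 = √[2p̄(1−p̄)/n] and s1 = √{[pT(1−pT) + pC(1−pC)]/n}, the chance of a one-sided win is Φ[(Δ − 1.96·s0)/s1].

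- Reading A (end of treatment): t = 7/10/14 against 7/7/10.
- Reading B (window, severe/critical read at Day 10 in both arms): t = 7/10/10 against 7/7/10.
- Reading C (one common day): same t in both arms.

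**Step 4. One case in full.** Reading A, median 7 days, mix 20/60/20. Conversion by Days 7, 10 and 14 is 0.500, 0.6285 and 0.750.

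- pT = 0.2×0.500 + 0.6×0.6285 + 0.2×0.750 = 0.627
- pC = 0.2×0.500 + 0.6×0.500 + 0.2×0.6285 = 0.526
- Δ = 0.1014, s0 = 0.0442, s1 = 0.0440
- Φ[(0.1014 − 0.0866)/0.0440] = Φ(0.336) = 0.63

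**Step 5. Mix 20/60/20 by median.**

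| Median (days) | A: rates, % | A: Δ | A: win | B: rates, % | B: Δ | B: win |
|---|---|---|---|---|---|---|
| 7 | 62.7 v 52.6 | +10.1 | 63% | 60.3 v 52.6 | +7.7 | 41% |
| 10 | 50.1 v 40.8 | +9.4 | 56% | 47.7 v 40.8 | +6.9 | 34% |
| 14 | 39.3 v 31.2 | +8.0 | 47% | 37.1 v 31.2 | +5.9 | 28% |
| 7/10/14 by type | 50.0 v 40.9 | +9.1 | 54% | 47.8 v 40.9 | +6.9 | 34% |

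**Step 6. Other mixes, medians 7-14 days.** Mix 60/30/10: 16-21% under A and 10-14% under B. Mix 80/15/5: 7-8% and 5-6%. All mild: 2.5%. Under reading C, Δ = 0 and the rate is about 2.5%.

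**Step 7. Checks.** In 40,000 simulated trials with fixed type counts (mix 20/60/20), the Miettinen-Nurminen score test at zero difference gives 47-64% (A), 28-42% (B) and 2.5-2.8% (C). A Mantel-Haenszel test stratified by type agrees within 1 point. The gap lies within type, so stratifying cannot remove it.

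**Step 8. Break-even.** Multiply the control clearance rate by r until the two weighted rates are equal. For mix 20/60/20, r = 1.33 under A and 1.24 under B. For 60/30/10 it is 1.15-1.17 and 1.12.

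**The case against.** The strongest reply is that Days 7-10 is one nominal visit shared by both arms. Several secondary indicators use the phrase that way, and the secondary RNA indicator lists Days 1, 3, 5 and 14, leaving out just that slot, as if the primary endpoint filled it. On that reading there is no bias. It is a plausible intention, but the protocol does not say it. The flow chart has Day 7 and Day 10 as separate visits, and the list of primary indicators gives only end of treatment. A statistical analysis plan could settle the matter, but this is not detail left for later: the protocol already states the time point, and does so in two ways that conflict.

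Other points qualify the size:

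- **Assumptions.** Mix, medians and curve are assumed, and the results run from 5% to 63% with them, mix above all. A nearly all-mild trial is the benign case. It is not the natural expectation, since entry requires the pneumonia diagnostic criteria and a SOFA score of at least 1, while mild type has no pneumonia on CT.
- **Permanence.** Inclusion criterion (5) covers patients whose RNA turned positive again. If all conversion probabilities are scaled by 0.8, the 47-63% falls to 36-44%, which is smaller but still large.
- **Hypothesis.** A false win presumes a test against zero difference. The text states neither superiority nor non-inferiority and gives no margin. Under non-inferiority these percentages would not be type I error rates, though the estimate would be shifted by the same amount.
- **Scope.** The figures concern one of three primary indicators, not the trial as a whole.

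**Conclusion.** The concern holds. As written, the endpoint has no single reading day. Its end-of-treatment wording reads carrimycin 3 days later in ordinary type and 4 days later in severe or critical type. Its window contradicts the 14-day course and still permits Day 10 against Day 7 in ordinary type. These facts come from the protocol alone, and the bias can only favour carrimycin as long as negativity rises with time.

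The size is illustrative. With equal, non-reversing exponential clearance and a test against zero difference, a mix dominated by ordinary type multiplies the nominal 2.5% by more than ten, whether each arm is read at end of treatment or within the window. A mostly mild mix still at least doubles it. If both arms were in fact read at one shared visit, the bias would vanish, and the protocol should then say so. The correction is needed before this endpoint can support a conclusion.

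**What to change.** Leave treatment durations as they are and reconcile the endpoint wording:

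1. In both the list of primary indicators and the efficiency analysis, replace the end-of-treatment and Days 7-10 wording with one study day, the same in both arms and for all types. Choose it from the RNA sampling days already in the flow chart (Day 10 or Day 14, for example) and make the other days supportive.
2. State that the swab is taken on that day whatever the course length. This matters for Day 10, which appears only among the medication-period columns, so a patient with a 7-day course might otherwise be thought to have no such visit.
3. Name the origin of the day count. Note 1 to the flow chart makes Day 0 the first day of administration, while the chart marks administration from Day 1.
4. If Day 14 is chosen, say which of the two Day 14 columns applies (medication period, or follow-up with ±1 day). Also edit secondary indicator (1), which already uses Day 14.

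The cost is wording and a firm instruction on the swab; sampling is already scheduled on Days 7, 10, 14 and 28 without arm distinction. There are two trade-offs. A later day raises conversion in both arms and may shrink the observed difference. Any common day also gives up the end-of-treatment concept, since some patients will still be on treatment and others already off it when read.
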